## PROTOCOL SYNOPSIS

Protocol Title:	Transfusion of Biotin-Labeled Red Blood Cells for the Evaluation of Genetic Factors that Contribute to Donor Differences in Red Blood Cell Storage and Post-Transfusion Red Blood Cell Recovery	
Protocol Number:	PRO19020356	
NCT Number:	NCT03364686	
Version # and Date:	Version 3.15/ April 30, 2021	
Clinical Phase:	Phase II Clinical Trial	
Investigational Product:	Biotin-Labeled Red Blood Cells (BioRBCs)	
Trial Site:	UPMC Montefiore Hospital [name]	
IND Sponsor:	[name] Chairman of the Department of Medicine Director, Pittsburgh Heart, Lung, Blood and Vascular Medicine Institute University of Pittsburgh, School of Medicine	
Investigator:	[name]	
Sub-Investigators:	[name], PhD [name]	[name] [name]
Study Monitor:	[name], IND Sponsor	
Research Facilities:	UPMC Montefiore Hospital Vitalant, Pittsburgh, PA	
Clinical Laboratories:	UPMC Presbyterian Shadyside CP PUH Hematopoietic Stem Cell Laboratory	
Study Rationale:	
As stored red cells age in cold storage, complex biochemical and metabolic alterations occur within the erythrocytes that results in hemolysis and reduced red cell post transfusion survival. Intravascular hemolysis following transfusion of aged stored red cells disrupt nitric oxide (NO) bioavailability, via accelerated NO scavenging reaction with cell-free plasma hemoglobin leading to worse outcomes. It remains unknown whether donor genetic background modulates this process.
 
In our recently completed large genome-wide association study (GWAS) study of red blood cell donors, we have identified a
	

	
number of single nucleotide polymorphisms (SNPs) that are associated with more red blood cell hemolysis in response to storage stress (storage, osmotic, or oxidative hemolysis). Examples of these SNPs may include sickle cell trait (AS), and single nucleotide polymorphisms (SNPs) in ankyrin 1 (ANK1), glucose-6-phosphate dehydrogenase X-linked (G6PD), piezo-type mechanosensitive ion channel component 1 (PIEZ01), spectrin alpha (SPTA), extended synaptotagmin-like protein 2 (ESYT2), Myo9b and SEC14. We hypothesize that these SNPs and others may affect the stability of red blood cells during storage and the recovery of red blood cells in the circulation after transfusion over 60 days. Additional variables that might affect red blood cell post-transfusion recovery include the donor sex and whether a donor is taking testosterone replacement therapy.
 
In general, the quality of a stored unit of red blood cells (RBC) is largely based on in vitro measures of hemolysis but the true quality of an RBC unit is based on the red cell ability to circulate through the vasculature and deliver oxygen to the tissues. Currently, there is limited data on the correlation between in vitro measures of hemolysis and post-transfusion in vivo survival of stored red blood cells. This project explores the gaps in knowledge between in vitro measures of hemolysis and in vivo lifespan of the RBC after transfusion.

Study Objectives:
	
The primary objective of this study is to define the post transfusion recovery of fresh or stored BioRBCs from blood donors who carry genetic mutations that can compromise RBC function and recovery in response to ex vivo cold storage and after transfusion into subjects.
 
The secondary objective is to define the effects of donors sex and testosterone replacement therapy on post-transfusion recovery and the correlation between in vitro correlates of the RBC storage lesion (e.g., storage and stress-induced hemolysis, membrane microvesicle formation) and post transfusion recovery of BioRBCs.

Study Hypothesis:
	
We hypothesize that genetic mutations and biologic variables (sex, race/ethnicity) in blood donors modulate the recovery of RBC after cold storage and transfusion.


Study Aims:
	
Aim 1: To explore the effect of selected SNPs on in-vitro measures of red cell biophysical properties, storage integrity, and post-autologous transfusion RBC recovery.
 
Aim 2: To examine the relationship between sex and sex hormones (testosterone) and in vitro markers of storage integrity and the in vivo 2-4 hours recovery and survival of RBCs stored under standard blood banking conditions.

Study Design:
	
The proposed clinical investigation will evaluate the in vivo lifespan of RBC in healthy volunteers after autologous transfusion over two different periods of storage. We will collect blood samples and label them with a naturally occurring vitamin, biotin. The RBCs will then be re-infused back into the same participant at 2 time points (5-7 days and 35-42 days after storage).
 
To evaluate RBC post transfusion survival, blood samples will be taken to quantify biotin labeled RBCs at 2-4 hours, 1 month and 2 months after each transfusion. On Day 125-150 post blood donation, subjects will be followed to evaluate anti-biotinylated RBC antibody formation. Throughout the study, subjects will be monitored carefully for occurrences of adverse events, laboratory test abnormalities, and changes in vital signs.
 
This protocol may cover up to (9) separate but similarly designed studies that may test 8 groups with candidate SNPs that were associated with hemolysis in REDS III Omics GWAS studies. Candidate SNPs may include, but are not limited to sickle cell trait (AS), and single nucleotide polymorphisms (SNPs) in ankyrin 1 (ANK1), glucose-6-phosphate dehydrogenase X-linked (G6PD), piezo-type mechanosensitive ion channel component 1 (PIEZ01), spectrin alpha (SPTA), and extended synaptotagmin-like protein 2 (ESYT2), Myo9B and SEC14. A subset of recalled donors with these SNPs will be asked to provide a blood sample to be tested for functional effects on red cell biophysical properties, stability in storage, and release of eDAMPs, and compared to donors with no implicated SNPs. We will develop an enriched SNP profile that defines a high risk and a low risk donor for further evaluation in autologous reinfusion studies as a low cost precision transfusion medicine array.
 
A 9th group of subjects on testosterone replacement therapy will also be evaluated.


Planned Sample Size:
	
Up to potentially 223 healthy volunteers (145 from RBC-OMICS + 78 from Biotin infusion )

Duration of Treatment:
	
The autologous reinfusion study consists of two blood transfusions of one day each separated by approximately one month.

Major Inclusion Criteria:
	
 
• Age 18 years or older
 
• Subjects will be selected based on having at least one SNP hypothesized to affect RBC transfusion storage and recovery. Controls will not have any of these SNPs. The eight genetic mutations may include sickle cell trait (AS), and single nucleotide polymorphisms (SNPs) in ankyrin 1 (ANK1), glucose-6-phosphate dehydrogenase X-linked (G6PD), piezo-type mechanosensitive ion channel
 

	
component 1 (PIEZ01), spectrin alpha (SPTA), extended synaptotagmin-like protein 2 (ESYT2), Myo9b and SEC14. We may identify additional SNPs as our analysis of the REDS-III GWAS study advances that could replace one of these SNP groups and/or we identify additional non-synonymous SNPs that are associated with susceptibility to hemolysis of stored red blood cells. In addition, we will evaluate 15 subjects on testosterone replacement therapy with 20 controls that are sex and race matched that are not on testosterone replacement therapy.
 
 
• Weight <math>\geq</math>110 lbs
 
• Hemoglobin <math>\geq</math> 12.5 g/dL or hematocrit <math>\geq</math> 38% for women and hemoglobin <math>\geq</math> 13.0 g/dL or hematocrit <math>\geq</math> 39% for men.
 
• Meet screening criteria for autologous blood donation
 


Major Exclusion Criteria:
	
 
• Subjects with a past medical history or symptoms of blood dyscrasia, diabetes mellitus, hyperlipidemia, obstructive sleep apnea, renal disease, congestive heart failure, significant cardiac disease and / or known peripheral arterial disease.
 
• Moderate to severe systemic hypertension (systolic blood pressure <math>></math>140 mmHg and/or diastolic blood pressure <math>></math> 95 mmHg
 
• Systolic blood pressure <math><</math>100 mmHg and/or diastolic blood pressure <math><</math> 60 mmHg on the study day.
 
• Positive Direct Antiglobulin Test (DAT)
 
• Consumption of biotin supplements or raw eggs within 30 days
 
• Previous or known allergy to biotin
 
• Treatment with antibiotics in the week before initiating study participation to avoid suppression of erythropoiesis, which may accompany infection.
 
• Blood loss in the previous 8 weeks due to epistaxis, trauma, hemoptysis, gastrointestinal bleeding, diagnostic phlebotomy (<math>></math>30ml).
 
• Subjects who report tobacco or marijuana smoking within 6 months of study.
 
• Cognitively impaired subjects, or institutionalized persons and subjects unable or unwilling to complete written informed consent
 
• Subjects with a history of blood donation within the previous 56 days.
 
• Use of other investigational drugs/devices within 30 days of screening.
 
• Subjects taking any medication for the treatment of diabetes including insulin
 
• Positive urine pregnancy test.
 
• History of prior transfusion reaction to blood products.
 

	
 
• Donors with naturally occurring antibodies against BioRBCs will be excluded from the study
 


Study Endpoints:
	
The primary endpoint is the labeled red blood cell recovery rate over 60-days post transfusion of 35-42 day stored Bio-RBCs from blood donors with specified genetic mutations, compared with control subjects without the specified mutation.
 
This protocol may evaluate up to eight (8) genetic mutations as independent studies, compared with pooled control groups (without any of the identified SNPs) as well as a group of subjects on testosterone replacement therapy. The eight genetic mutations may include sickle cell trait (AS), and single nucleotide polymorphisms (SNPs) in ankyrin 1 (ANK1), glucose-6-phosphate dehydrogenase X-linked (G6PD), piezo-type mechanosensitive ion channel component 1 (PIEZ01), spectrin alpha (SPTA), extended synaptotagmin-like protein 2 (ESYT2), Myo9b and SEC14. All control subjects will be tested and must not have any of these SNPs. We may identify additional SNPs as our analysis of the REDS-III GWAS study advances that could replace one of these SNP groups and/or we identify additional non-synonymous SNPs that are associated with susceptibility to hemolysis of stored red blood cells. In addition, we will evaluate 15 subjects on testosterone replacement therapy with 20 controls that are gender and race matched that are not on testosterone replacement therapy.
 
The secondary endpoints include effects of gender on post transfusion recovery, the 2-4 hours post transfusion survival of fresh or stored Bio-RBCs, and to determine the association between in vitro correlates of the RBC storage lesion (e.g., storage and stress-induced hemolysis, membrane microvesicle formation) and post transfusion recovery.
 
A subset of recalled donors with these SNPs will be asked to provide a blood sample to be tested for functional effects on red cell biophysical properties, stability in storage, and release of eDAMPs, and compared to donors with no implicated SNPs. We will develop an enriched SNP profile that defines a high risk and low risk donor for further evaluation in autologous reinfusion studies as a low cost precision transfusion medicine array.

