## **2.4 STUDY ENDPOINTS**

### Primary Endpoint:

The primary endpoint is the labeled red blood cell recovery rate over 60-days post transfusion (using data from 2-4 hours, 1 and 2 month) of 35-42 day stored Bio-RBCs from blood donors with specified genetic mutations, compared with control subjects without the specified mutation.

This protocol may evaluate up to eight (8) genetic mutations as independent studies, compared with pooled control groups, as well as a group of subjects on testosterone replacement therapy. The eight genetic mutations that we will evaluate may include sickle cell trait (AS), and single nucleotide polymorphisms (SNPs) in ankyrin 1 (ANK1), glucose-6-phosphate dehydrogenase X-linked (G6PD), piezo-type mechanosensitive ion channel component 1 (PIEZ01), spectrin alpha

(SPTA), extended synaptotagmin-like protein 2 (ESYT2), Myo9b, and SEC14. We may identify additional SNPs as our analysis of the REDS-III GWAS study advances that could replace one of these SNP groups and/or we identify additional non-synonymous SNPs that are associated with susceptibility to hemolysis of stored red blood cells. In addition we will evaluate 15 subjects on testosterone replacement therapy with 20 controls that are gender and race matched that are not on testosterone replacement therapy. Each group will be considered a separate study for statistical purposes. Controls will be selected based on not having any of the SNPs that will be evaluated in these studies.

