## 2.5 STATISTICAL ANALYSIS

### 2.5.1 Sample Size Determination

In healthy volunteers, the mean (SD) of 30 and 60-days RBC biotin recovery rate is 75% (12.5%) and 50% (10%) (calculated from 24-hour 100% recovery value), respectively. For our first study, evaluating patients with the sickle cell trait SNP, we expect SCD trait to reduce 30 and 60-day recovery to 62% and 25%. A sample size of 15 subjects with sickle cell trait (HbAS) and 20 control African American subjects (HbAA; 10 males and 10 females) would provide 84% power to detect a difference of 13% (SD =12.5%) for 30 days and a power of >95% to detect a difference of 25% (SD = 12.5%) for 60 days RBC recovery rate between AS and AA. This sample size has at least 80% power to detect the interaction between time and genetic group as measure of different recovery rate. We will also recruit an additional 20 Caucasian control (HbAA, 10 males and 10 females) to gain power for testing the effect of other RBC mutations identified in our genome-wide association studies of blood donors (NHLBI RBC-Omics). We will use explanatory analysis for the evaluation of post transfusion recovery of RBCs from subjects with rare variants (<10% of the population) due to a projected small number of subjects carrying such mutations. All 40 control subjects will be tested and selected to not have any of the SNPs that we are studying (listed below).

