#### Healthy African American volunteers with sickle cell trait ( subjects who complete the study=15)

- Self-identification of African American race
- Sickle cell trait (HbAS) status confirmed by hemoglobin electrophoresis

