#### Healthy volunteers enrolled in REDS-III Red Blood Cell Omics (RBC-Omics) study (105=subjects who complete the study)

- Recalled blood donors from the RED-III RBC-Omics study with non-synonymous SNPs identified in ANK1, G6PD, PIEZ01, SPTA, ESYT2, Myo9b, SEC14 and/or we identify additional non-synonymous SNPs that are associated with susceptibility to hemolysis of stored red blood cells. We may identify additional SNPs as our analysis of the REDS-III GWAS study advances that could replace one of these SNP groups. The SNPs will be tested for functional effects on red cell biophysical properties, stability in storage, and release of eDAMPs, compared to donors with no implicated SNPs. We will develop an enriched SNP profile that defines a high risk and low risk donor for further evaluation as a low cost precision transfusion medicine array. As determined in the aforementioned primary and secondary endpoints.

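### Controls must be free of every candidate SNP, but study subjects may carry non-index variants, so a group difference may not belong to the index variant or to testosterone alone

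*Combined protocol and SAP*

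**What the plan says.** **Controls.** The rule covers all candidates and appears in several places. The Synopsis (Study Endpoints) says "All control subjects will be tested and must not have any of these SNPs". Section 2.4 says "Controls will be selected based on not having any of the SNPs that will be evaluated in these studies". Section 2.5.1 says "All 40 control subjects will be tested and selected to not have any of the SNPs that we are studying".

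**Study groups.** No matching rule appears.
- Synopsis, Major Inclusion Criteria: selection is based on "having at least one SNP hypothesized to affect RBC transfusion storage and recovery. Controls will not have any of these SNPs". For study subjects this does not say exactly one.
- Section 3.2, sickle-trait group: self-identified African American race and "Sickle cell trait (HbAS) status confirmed by hemoglobin electrophoresis". Nothing is said about the other seven variants.
- Section 3.2, RBC-Omics group: "Recalled blood donors from the RED-III RBC-Omics study with non-synonymous SNPs identified in ANK1, G6PD, PIEZ01, SPTA, ESYT2, Myo9b, SEC14", with provision for further SNPs. Carrying more than one is not barred.
- Section 3.2, testosterone group: male sex is the only added criterion.
- Section 3.3 and the Synopsis exclusions contain no genotype criterion.

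**Analysis.** Section 2.4 treats each group as a separate study. Section 2.5.2 fits time, genetic group and their interaction, and declares significance at P<0.05. Visit 1 (Section 2.2.2, Appendix A) includes genetic testing for infusion subjects, and Section 2.2.1 has subgroup samples analysed for all the listed SNPs. No text uses those results to exclude or adjust within a study group.

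**The concern.** The two sides of each comparison are selected by different genetic rules. A volunteer with HbAS and a G6PD SNP can enter the sickle-trait group, while an HbAA volunteer with the same G6PD SNP is refused as a control. If the G6PD SNP lowers recovery, part of that loss is counted as a sickle-trait effect.

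The same holds for a man on testosterone who carries a candidate variant, if his controls come from the SNP-free pool. That step is an inference. The testosterone sentences mention only gender and race matching, but the SNP-free rule is worded for all controls, and the infusion roster in Section 2.5.1 lists no separate testosterone controls.

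At stake is attribution. A variant or therapy with no effect of its own could be reported as significantly harmful, or a real effect could be overstated.

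**Working it through.** **Inputs from the plan (Section 2.5.1):** 15 study subjects versus 20 controls; SD 12.5 points; expected sickle-trait differences of 13 points at 30 days and 25 points at 60 days; stated power 84% for the 30-day difference. Section 2.5.2 gives the 0.05 level; two-sided testing is assumed.

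**Plan's own figure.** Standard error = 12.5 × √(1/15 + 1/20) = 4.27. Noncentrality = 13/4.27 = 3.04 on 33 degrees of freedom. Two-sided t-test power = 84.0%, so the stated 84% reproduces.

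**Assumptions, because the plan gives no figures:** seven other variants, independent, each carried by a fraction p of eligible people. Carrying any of them lowers recovery by e points. The index factor has no effect. Controls carry none. A two-sample t-test at one time point stands in for the mixed model.

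**Formulas.** Share of study subjects with another variant: s = 1 − (1 − p)^7. Bias = s × e. The false-positive rate comes from simulated t-tests, 15 versus 20, at least 20,000 per setting.

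| p per variant | s | of 15 | bias, e = 5 | false positives, e = 5 | bias, e = 13 | false positives, e = 13 |
|---|---|---|---|---|---|---|
| 2% | 13% | 2.0 | 0.7 | about 5% | 1.7 | about 7% |
| 5% | 30% | 4.5 | 1.5 | about 6% | 3.9 | about 14% |
| 10% | 52% | 7.8 | 2.6 | about 9% | 6.8 | about 31% |

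The 13-point column borrows the plan's 30-day sickle-trait difference as a per-variant effect. The 5-point column is an assumed weaker effect.

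**Sensitivity.** If each extra variant costs e separately, so that two cost 2e, the rates at p = 2%, 5% and 10% become about 5%, 7% and 13% for 5 points and 7%, 16% and 44% for 13 points. For testosterone all eight variants are non-index; the additive 13-point rates are then about 7%, 19% and 54%.

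**Where these sizes apply.** Section 2.5.1 lists 15 HbAS and 15 testosterone infusion subjects, but only 20 infusion subjects with RBC-Omics SNPs in total. Over seven SNPs that is 20/7, or about 3 each. The table therefore fits the sickle-trait and testosterone comparisons, not the SNP arms.

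**Cost of restricting to single-factor subjects (SD 12.5, 13-point difference).**
- 13 versus 20 (p = 2%): standard error 4.45, noncentrality 2.92, power about 81%.
- 7 versus 20 (p = 10%): standard error 5.49, which is 5.49/4.27 = 1.29 times the planned one; noncentrality 2.37, power about 62%.
- 7 versus 20 for the plan's 25-point 60-day difference: noncentrality 25/5.49 = 4.55, power about 99%.

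**The case against.** The strongest reply is that the clean-control rule is deliberate. One pooled control set serves up to eight studies in a single-center pilot whose first aim is exploratory, and letting controls carry non-index variants would shrink that set for those variants' own comparisons. This stands, and it is why the fix leaves the controls alone. It does not answer the attribution problem, since results will still be declared significant at 0.05 for each factor.

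Several stronger readings are tempting and do not hold.
- *The bias always runs toward worse recovery.* The SNPs were picked for association with hemolysis, and the protocol only hypothesises an effect on recovery. A second variant without effect gives no bias, and a protective one reverses it.
- *The endpoint contradicts the control rule.* The endpoint says "compared with control subjects without the specified mutation", but donors free of all candidates are also free of the specified one, and the next Synopsis paragraph describes the pooled controls that way.
- *The enriched SNP profile favours multi-SNP carriers.* The profile is undefined and covers both high-risk and low-risk donors.
- *The selection rule invites co-carriers into every comparison.* It may only describe the pooled carriers, since the visit text in Section 2.2.2 speaks of subjects with one of the targeted SNPs. Still, nothing in the criteria excludes a co-carrier.
- *The 25-point sickle-trait effect can be given to the other variants.* The plan gives no effect for any other variant, and sickle trait is not an *other* variant in its own comparison.

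**Conclusion.** The asymmetry is plain in the text, and neither eligibility nor the model removes it. For testosterone it rests on the inference that the general control rule applies.

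Its effect is conditional. The difference is biased toward lower recovery in the study group only if the other variants are harmful. The size cannot be fixed from the documents. Under the stated assumptions it runs from negligible (about 5% false positives at 2% carriage and 5 points) to serious (about 31% at 10% carriage and 13 points). A reader might infer that all eight genetic comparisons face the upper figures; the roster does not support that for the SNP arms.

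The point merits a change because the genotypes are already being collected, not because a large bias has been shown.

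**What to change.** 1. Use the Visit 1 genotypes to report how many subjects in each study group carry a non-index candidate variant.
2. Prespecify for each comparison an analysis restricted to study subjects with no other candidate variant, so that both sides meet the same rule.
3. Attribute a difference to the single variant, or to testosterone, only if that analysis supports it. Otherwise describe the contrast as carriers (or testosterone users) versus donors free of all candidate variants.
4. Do not rely on a covariate for other SNPs while controls carry none: their effects would be estimated only within the 15 study subjects.
5. If an SNP is added or swapped in, genotype it in already enrolled subjects on both sides before that comparison is run.

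The cost is analysis-plan wording, plus genotyping of enrolled subjects if item 5 arises. The statistical price is precision in the restricted analysis: slight if co-carriage is rare (about 81% power for 13 points) and substantial if it is common (about 62%, against 84% planned). The planned comparison on all subjects can stay beside it under the broader description.
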